8.0 EVALUATION OF SAFETY PARAMETERS

The safety population will be used for all safety analyses.

8.1 SERIOUS ADVERSE EVENTS AND ADVERSE EVENTS OF INTEREST

Only SAEs and AEs of special interest will be evaluated for this study. AEs of special interest will include a) severe localized injection site reactions and severe systemic reactions that occur from Day 0 to Day 7 and b) severe clinically significant changes in hematology between screening and Week 4. SAEs will be recorded from administration of the investigational product at the vaccination visit through the follow-up phone call at Week 26. AE data will be coded using MedDRA v22.0.

Severe localized injection site reactions and severe systemic reactions that occur from Day 0 to Day 7 will be summarized by category (localized or systemic) and maximum severity. An overall summary with point estimates of incidence and 95% confidence intervals will be provided for severe localized injection site reactions and severe systemic reactions, along with average durations for each. Clinically significant changes in hematology between screening and Week 4 and related SAEs will also be summarized by maximum severity.

A summary of all SAEs by system organ class and preferred term will be produced. A similar summary will be produced for SAEs that are categorized as NOCIs (serious NOCIs). Summaries by maximum severity and strongest relationship to vaccine will be produced for all SAEs. SAEs, serious NOCIs, severe localized injection site reactions and severe systemic reactions, clinically significant changes in hematology between screening and Week 4, AEs resulting in death, and AEs leading to discontinuation from the study will be provided in appendix listings of the clinical study report.

When calculating the incidence of AEs, each AE will be counted only once for a given participant within a MedDRA category (e.g., overall, system organ class, or preferred term). When AEs are summarized within levels of another AE assessment (e.g., causality or severity), AEs will be counted once per participant at the worst level of the assessment (e.g., strongest relationship to study drug or greatest severity).

8.2 CLINICAL LABORATORY EVALUATIONS

Samples for hematology, serum chemistry, and urinalysis will be collected at screening. Hematology samples will also be collected at Week 4.

Treatment-emergent abnormal hematology values at Week 4 will be summarized. Hematology laboratory abnormalities will be assessed for relatedness and may be presented by relatedness in tables based on the investigator's assessment.

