5.2.2.2 Plasma Donation Period (up to 14 weeks)

After receiving the rBV A/B vaccination, the participant may participate as a source plasma donor if they choose. A screening physical exam will be performed at the plasma collection center. Donor eligibility will be determined at the sponsor-approved, licensed source plasma collection center. Once donor eligibility has been confirmed, the participant may begin donating plasma 1 week after vaccination up to twice a week for the next 12 weeks, with the possibility of continuing for up to 14 weeks, consistent with FDA plasma donation regulations and guidelines.^[2]

During the first visit to the plasma collection center, the following activities will occur:

- Brief physical examination by a licensed physician or otherwise authorized designee at the plasma collection center (the medical exam for plasmapheresis is repeated on an annual basis)
- Measurement of vital signs (temperature, blood pressure, heart rate, and respiratory rate)
- Obtaining informed consent for plasma donation and procedures
- Completion of donor history questionnaire (Appendix D)
- Finger prick for hemoglobin measurement and total serum protein measurement
- Approximately 10 mL of whole blood collected for atypical antibody measurements, serologic test for syphilis, and serum protein electrophoresis at 4-month intervals
- Obtaining 20 mL whole blood by side sample collections for NAC determination
- Plasma donation (takes approximately 1 to 1.5 hours) per the donation site's procedures
- Each donated unit will be tested for infectious markers using nucleic acid testing

During each subsequent visit to the plasma collection center, the following activities will occur:

- Completion of the donor history questionnaire
- Measurement of vital signs (temperature, blood pressure, heart rate, and respiratory rate)
- Finger prick for hemoglobin measurement and total serum protein measurement
- Obtaining 20 mL whole blood by side sample collections for NAC determination

- Plasma donation (takes approximately 1 to 1.5 hours) per the donation site's procedures
- Each donated unit will be tested for infectious markers using nucleic acid testing

Samples for NAC determination will be obtained before plasma collection. The source plasma from plasmapheresis will be retained and is eligible for use in the production of BabyBIG.

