1.3 STUDY DESIGN

This will be an open-label, uncontrolled study to evaluate the safety and immunogenicity of a single intramuscular injection of 40 µg of rBV A/B in participants who were previously immunized with PBT (or PBT and rBV A/B) for occupational protection. Participants will receive the rBV A/B injection and may elect to undergo plasmapheresis at a maximum of two times per week for up to 12 weeks post-vaccination. Participants continue plasmapheresis for up to 14 weeks post-vaccination as long as they continue to meet source plasma donor acceptance criteria.

The study period is defined as the 12-week period that includes the clinic visits and plasmapheresis visits. The study period will end at Week 4 for participants who opt not to participate or who have been determined to be ineligible for donation for the entire study. Participants undergoing plasmapheresis will also have an additional hematology specimen collected at Week 4 and will have a final on-site study visit at Week 12. All participants will have a final phone call for safety follow-up at Week 26.

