1.6 STUDY PROCEDURES

The study will begin with a 7-day screening period (Days -7 to -1), during which participant eligibility will be determined. Screening must occur 1 to 7 days before the Vaccination Visit (Day 0).

Participants will enter either a 4-week treatment period (for non-plasma donors) or a 12-week treatment period (for plasma donors). At the Vaccination Visit (Day 0), the first day of the treatment period for all subjects, participant eligibility will be reviewed and blood collection will be performed to determine baseline NAC. After these assessments, a single rBV A/B injection will be administered to stimulate the production of antibodies against botulinum toxin type A and type B. Safety assessments will be performed before and after the injection, and a diary will be distributed to the participant to record injection site information, systemic reactions, and concomitant medications over the next seven days.

Study personnel will call all participants at Week 1 (\pm 3 days) to review the diary, injection site reactions, and any potential serious adverse events (SAEs) or new onset chronic illnesses (NOCIs) occurring over the past week.

Participants who receive the rBV A/B vaccination may elect to participate as source plasma donors if they meet the donor eligibility criteria of the sponsor-approved licensed source plasma collection site. Participants who elect to donate source plasma may begin following the Week 1 safety phone call and may donate up to twice per week through Week 12, with the possibility of continuing through Week 14 post-vaccination if they continue to meet source plasma donor eligibility criteria. The assessments to be completed at the visits to the plasma collection center are listed in the protocol and include a blood collection for NAC determination.

Safety assessments for non-plasma donors are scheduled on Week 0, Week 1 (\pm 3 days) (by phone), and Week 4 (\pm 3 days) (final on-site visit). Safety assessments for plasma donors are scheduled at Week 0 with follow-up phone calls at Weeks 1 (\pm 3 days), 4 (\pm 3 days) and 10 (\pm 3 days), and a final on-site study visit at Week 12 (\pm 7 days) to assess general health status and query for the interim occurrence of SAEs or NOCIs, if any.

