2.1.3 Safety Population

The safety population will include all participants enrolled into the study who receive the vaccine dose and have at least one post-baseline safety assessment [this assessment can include a response from a participant that no adverse events (AEs) occurred].

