2.1.3 Plasma-Donating Population

The plasma-donating population will include all participants who receive the vaccine and donate at least one plasma unit. This population will be used for the exploratory endpoint described in Section 9.0.

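### The Week 4 hematology summaries pool plasma donors with non-donors, so they cannot separate changes after vaccination from changes due to donation

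*SAP*

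**What the plan says.** SAP 8.0 sets one analysis set: "The safety population will be used for all safety analyses". The definition takes in donors and non-donors alike: "The safety population will include all participants enrolled into the study who receive the vaccine dose and have at least one post-baseline safety assessment". The SAP also defines a plasma-donating population, but gives it a single use: "This population will be used for the exploratory endpoint described in Section 9.0", which is the volume of plasma collected.

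Week 4 hematology appears in two summaries. SAP 8.2 says "Treatment-emergent abnormal hematology values at Week 4 will be summarized". SAP 8.1 says "Clinically significant changes in hematology between screening and Week 4 and related SAEs will also be summarized by maximum severity". Neither is broken down by donor status or number of donations. SAP 8.2 goes on to require that hematology abnormalities be assessed for relatedness, but leaves presentation by relatedness optional.

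On exposure, SAP 1.6 says that participants who elect to donate "may begin following the Week 1 safety phone call and may donate up to twice per week through Week 12". Protocol 5.2.2.2 lists, for the first and each later visit to the plasma center, "Obtaining 20 mL whole blood by side sample collections for NAC determination". It adds about 10 mL at the first visit for other tests. Table 1 in both documents labels the plasmapheresis column Weeks 2 to 14. The one scheduled post-vaccination hematology panel for donors is at Week 4 (SAP 1.3: "Participants undergoing plasmapheresis will also have an additional hematology specimen collected at Week 4"). Non-donors have theirs at the Week 4 site visit (Protocol 5.2.2.4).

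**The concern.** The interval from screening to Week 4 contains vaccination for everyone. For donors it can also contain several plasmapheresis sessions and the blood drawn at each. The protocol itself treats donation as relevant to hemoglobin: hemoglobin is checked at every plasma visit, and donation continues only while it stays in range (Table 1, note o).

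The study is uncontrolled, so the only internal contrast between vaccination alone and vaccination plus donation is between non-donors and donors. The planned tables remove that contrast. If mild hemoglobin abnormalities appear at Week 4, the clinical study report will show one pooled frequency, and its readers will not be able to tell from the table whether the abnormalities cluster in people who were giving plasma.

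**Working it through.** The documents give no expected rate of hematology abnormalities and no power calculation, so there is no planned figure to reproduce. The check has four steps.

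**1. Donations possible before the Week 4 draw.** The inputs are at most two donations per 7-day block and a draw on Day 25, 28 or 31 (Day 28 ± 3). The ± 3 days is stated for the Week 4 calls and the non-donor visit; applying it to the donors' draw is an assumption. I also assume that the two donations in a block are at least 2 days apart and that none falls on the draw day, because the documents do not say whether the draw precedes a donation. The counts are maxima at full frequency.

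- Start on Day 7 (1 week after vaccination): 6, 6 and 8 donations for draws on Days 25, 28 and 31.
- Start on Day 14 (Table 1's Week 2, read as Day 14): 4, 4 and 6 donations.

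**2. Protocol-specified whole blood taken.** Volume = 20 mL × donations + 10 mL at the first visit.

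- 4 donations: 20 × 4 + 10 = 90 mL
- 6 donations: 20 × 6 + 10 = 130 mL
- 8 donations: 20 × 8 + 10 = 170 mL

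A non-donor has no protocol blood draw after Day 0 until the Week 4 draw itself.

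**3. What that could do to hemoglobin.** Fall = hemoglobin × volume drawn ÷ blood volume. Assumptions not in the documents are hemoglobin of 14 g/dL, blood volume of 4 to 6 L and no red-cell replacement.

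- Smallest: 14 × 90 ÷ 6000 = 0.21 g/dL
- Largest: 14 × 170 ÷ 4000 = 0.595 g/dL

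The range is about 0.2 to 0.6 g/dL, before any effect of the procedure itself. Set this against Protocol Appendix B, Table 9, and the donor limits in Appendix A:

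- Grade 1 for men is 12.5-13.5 g/dL and the male donor limit is 13.0 g/dL. A man screened at 13.6 g/dL would fall by 13.6 × 90 ÷ 6000 = 0.20 to 13.6 × 170 ÷ 4000 = 0.58 g/dL and end between 13.4 and 13.02 g/dL. He becomes a new Grade 1 value while still eligible to donate.
- Grade 3 starts at 10.4 g/dL for men and 9.4 g/dL for women. From the lowest donor limits the distance is 13.0 − 10.4 = 2.6 g/dL for men and 12.0 − 9.4 = 2.6 g/dL for women. A fall of 0.6 g/dL comes nowhere near.

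**4. What pooling does to the table (illustration).** Let f be the donor share, p_d the abnormality rate in donors and p_n the rate in non-donors. Pooled rate = f·p_d + (1 − f)·p_n, and the share of counted abnormalities that is donor excess = f·(p_d − p_n) ÷ pooled rate. All three inputs are assumed.

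| f | p_n | p_d | Pooled rate | Donor-excess share |
|---|---|---|---|---|
| 20% | 2% | 10% | 3.6% | 44% |
| 20% | 5% | 20% | 8.0% | 38% |
| 50% | 2% | 10% | 6.0% | 67% |
| 80% | 5% | 30% | 25.0% | 80% |

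Across the nine combinations tried (f of 20%, 50% and 80%, with these three pairs of rates), the pooled rate runs from 3.6% to 25% and the donor-excess share from 38% to 80%. A pooled figure alone does not show which case applies.

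**The case against.** A reader might infer that the plan counts donation effects as vaccine effects. It does not. Treatment-emergent is a timing label, and SAP 8.2 and Protocol 8.2.5 both require abnormalities to be assessed for relatedness. What remains is that presentation by relatedness is optional, and the causality guidance in Protocol 6.4 is written for SAEs and does not name plasmapheresis. The table as planned may therefore carry no such information.

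A reader might also infer that the hematology safety endpoint or the stopping rule is biased. The documents do not support that. The endpoint concerns changes resulting in severe or serious events (Protocol 3.3.2, SAP 3.2.2). The stopping rule counts similar Grade 3 or higher abnormalities judged at least possibly vaccine-related (Protocol 4.4.2). A fall of 0.2 to 0.6 g/dL does not produce these, and the hemoglobin check at each donation makes a large donation-caused fall less likely.

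A third tempting step is to treat non-donors as the clean estimate of the vaccine effect. That would bring in selection bias. Non-donors include people found ineligible to donate (Protocol 3.1), low hemoglobin is one ground for ineligibility (Appendix A), and continuing to donate depends on hemoglobin measured after vaccination. The strata are self-selected and partly sorted on the outcome.

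It can fairly be added that the donation counts are ceilings, that only hemoglobin has a worked mechanism here, and that with at most 50 participants a reader could match listings by hand, since plasmapheresis data and clinically significant hematology changes are both listed. All of this stands and limits the weight of the point. It does not make the pooled summary informative.

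**Conclusion.** The point holds as a limited one. The planned Week 4 hematology summaries mix vaccination alone with vaccination plus up to about 4 to 8 plasmapheresis sessions and roughly 90 to 170 mL of sampled whole blood, and nothing in SAP 8.1 or 8.2 separates them.

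The consequence falls mainly on Grade 1-2 values, especially hemoglobin, in the SAP 8.2 summary. By the arithmetic above, blood sampling alone reaches chiefly Grade 1; Grade 2 would generally need a further effect of the procedure, which the documents do not quantify. No bias in the severe or serious endpoint or in the stopping rule has been shown.

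The size rests on assumed blood volume, starting hemoglobin, no red-cell replacement, donation at full frequency and the draw-day range. Donor share and abnormality rates are not stated in the documents, so the mixture figures are illustrative. The count also depends on an unresolved inconsistency over when plasmapheresis starts.

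**What to change.** In SAP 8.1 and 8.2, present Week 4 hematology (change from screening and grade shifts) overall and separately for participants with no donation and with at least one donation before the Week 4 draw. List the number of donations before the draw beside each abnormal value.

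Report both strata descriptively. State that they are small, self-selected and partly sorted by donor eligibility, including hemoglobin, and do not rest vaccine statements on the non-donor stratum alone.

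Reconcile the text that starts plasmapheresis 1 week after vaccination (Protocol 5.1 and 5.2.2.2; SAP 1.6 has it follow the Week 1 call) with the Week 2 to 14 column in Table 1 of both documents, since this sets the exposure before Week 4.

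The cost is one by-group descriptive table and one listing column. SAP 9.0 already summarizes and lists plasmapheresis data. The price is low precision. With illustrative counts, the exact 95% interval is 3.3% to 21.8% for 5/50 pooled, 6.8% to 40.7% for 5/25 donors, 0% to 13.7% for 0/25 non-donors and 0% to 30.8% for 0/10 non-donors.

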8.3 PRIOR AND CONCOMITANT MEDICATIONS

All prior and current medications taken within 60 days prior to Screening will be collected and recorded in the eCRF. Concomitant medications will be queried for at each visit. Concomitant medication data will be listed.

8.4 VITAL SIGNS AND OTHER PHYSICAL EXAMINATIONS

Vital sign measurements will include temperature, blood pressure, heart rate, and respiratory rate. These measurements will be provided in an appendix listing of the clinical study report.

Physical examinations will be performed during screening and at the initial plasmapheresis visit. Physical examination findings will be recorded with medical history or AEs.

8.5 PARTICIPANT DIARIES

Participants will complete a home diary on a daily basis for 7 days post-vaccination, as well as during the study period to report any adverse events and concomitant medications. Significant data from the diaries will be additionally recorded with adverse event data or concomitant medication data, so there will be no separate summaries or listings of diary data.

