E-mail : [contact]

Medical monitor:

[name] [name]., F.A.C.P.
Clinical Professor, Emeritus
UCB-UCSF Joint Medical Program
Chair, Editorial Board, UC Berkeley *Wellness Letter*
University of California, Berkeley
[name]
[contact]
[contact]
E-mail: [contact]

STUDY SYNOPSIS

Name of sponsor company: California Department of Public Health (CDPH)	
Name of investigational product: Recombinant Botulinum Vaccine A/B (rBV A/B)	
Names of active ingredients: Recombinant Botulinum Antigen A and Antigen B adsorbed to 0.2% (wt/vol) Alhydrogel™	
Title of study: Tolerability and Immunogenicity of a Single 40- μ g Dose of Recombinant Botulinum Vaccine A/B (rBV A/B) for the Production of BabyBIG® in Volunteers with Existing Botulinum Immunity	
Sponsor Investigator: [name]	
Number of sites: 2	
Study period: 18 months	Phase of development: Phase 2
Objectives:	
Immunogenicity: The immunogenicity objective of this study is to evaluate the effects of a single 40- μ g dose of the recombinant botulinum vaccine A/B (rBV A/B) on botulinum toxin type A and type B neutralizing antibody concentration (NAC) over a 12-week period following vaccination in participants who have previously been immunized with pentavalent botulinum toxoid (or pentavalent botulinum toxoid and rBV A/B) for occupational protection.	
Safety: The safety objective of this study is to obtain safety information during the 12-week study period and at 6 months post-vaccination on the use of rBV A/B in a population of participants previously immunized with pentavalent botulinum toxoid (or pentavalent botulinum toxoid and rBV A/B) for occupational protection.	
Exploratory: The exploratory objective of this study is to collect source plasma from participants that contains neutralizing antibodies against botulinum toxin type A and type B for the production of BabyBIG .	
Methodology: This Phase 2, open-label, uncontrolled study designed to evaluate safety, tolerability, and immunogenicity of a single dose of rBV A/B in healthy participants previously immunized with pentavalent botulinum toxoid (or pentavalent botulinum toxoid and rBV A/B) for occupational protection will be conducted to collect source plasma for potential use in the production of BabyBIG and to evaluate safety and immunogenicity of the vaccine in these participants over a 12-week period, with a follow-up safety assessment at 6 months.	

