6.9 INJECTION SITE AND SYSTEMIC REACTIONS

Commonly seen injection site reactions for rBV A/B are consistent with reactions in participants vaccinated with other recombinant protein vaccines that include Alhydrogel™. The majority of reactions at the injection site seen to date with rBV A/B have been mild or moderate in severity and included erythema, pain, pruritus, and swelling. Participants will be actively monitored for localized and systemic reactions to the injections and an anaphylaxis (epinephrine) kit will be available at the time of injections.

The definitions to be used to determine severity of injection site reactions are provided in [Table 5](#).

Table 5. Protocol Definitions for Severity of Injection Site, ie., Local Reactions

Local Reaction to Injectable Product	Mild (Grade 1)	Moderate (Grade 2)	Severe (Grade 3)	Potentially Life-Threatening (Grade 4)
Injection site pain	Does not interfere with activity	Repeated use of nonnarcotic pain reliever >24 hours or interferes with activity	Any use of narcotic pain reliever or prevents daily activity	ER visit or hospitalization
Injection site tenderness	Mild discomfort to touch	Discomfort with movement	Significant discomfort at rest	ER visit or hospitalization
Injection site erythema (redness) ^a	2.5-5.0 cm	5.1-10.0 cm	>10.0 cm	Bullae, necrosis, or exfoliative dermatitis
Injection site swelling (induration) ^b	2.5-5.0 cm and does not interfere with activity	5.1-10.0 cm or interferes with activity	>10.0 cm or prevents daily activity	Necrosis

ER = emergency room.

^a In addition to grading the measured local reaction at the greatest single diameter, the measurement should be recorded as a continuous variable.

^b Induration (swelling) should be evaluated and graded using the functional scale as well as the actual measurement.

Systemic reactions collected in the diary are severity of muscle weakness, malaise, rash, headache, nausea, chest discomfort, breathing difficulties, anxiety, feelings of depression, and neuromuscular TEAEs. For systemic reactions, use the guidance provided in Appendix B.

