1.4 SAMPLE SIZE

No formal power calculations were performed for this study. The sample size will consist of up to 50 participants. On the basis of prior Sponsor-Investigator experience, this sample size is considered adequate for fulfilling the study objectives.

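### The protocol limits reaction reporting to severe or serious events and SAP 8.5 follows it, so the mild and moderate reactions in every participant's 7-day diary go unreported

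*SAP*

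**What the plan says.** **What is collected.** The diary form (Protocol Appendix C) asks for daily entries on Days 1 to 7. Soreness, itching and nine systemic items are answered yes or no; erythema and induration are measured in mm with a supplied tool. Staff go through the diary at the Week 1 call (Protocol 5.2.2.3). Table 5 in Protocol 6.9 defines Grades 1 to 4 for local reactions, and its note a says of the local reaction diameter that "the measurement should be recorded as a continuous variable".

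**What is analysed.** SAP 8.5 moves only the diary items it regards as significant into the event or medication records. For everything else its rule is: "so there will be no separate summaries or listings of diary data". It does not define significant. SAP 8.1 restricts adverse event evaluation to SAEs and events of special interest. For reactions in Days 0 to 7 it says: "An overall summary with point estimates of incidence and 95% confidence intervals will be provided for severe localized injection site reactions and severe systemic reactions".

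**Where the restriction starts.** The protocol synopsis (safety considerations) gives the diary's purpose as finding severe or serious events and names severe reactions for eCRF entry. Protocol 3.3.2 limits the reaction endpoints to severe reactions and SAEs. Protocol 6.6 limits reactions of special interest to severe ones, and Protocol 8.2.5 summarises only severe AEs and SAEs from the Week 1 call.

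**What the trial says it is for.** Tolerability is the first word of the title. The synopsis methodology describes a study "designed to evaluate safety, tolerability, and immunogenicity of a single dose of rBV A/B in healthy participants", and SAP 1.1 also says the study continues the evaluation of tolerability.

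**The concern.** Tolerability of a vaccine is described mainly by its common reactions: how many people have a sore arm or feel unwell, for how long, and how large the redness and swelling become. Protocol 6.9 says most injection site reactions seen to date were mild or moderate, and Protocol 1.3 says most treatment-emergent events were mild and transient. The plan therefore reports none of the grades in which it expects most reactions, even though every participant records them.

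Two features of this trial add weight. Some participants will receive rBV A/B again after a dose in the earlier study (Protocol 1.2), and Protocol 8.2.4 mentions a possible further booster, so reactions on re-dosing are of practical interest. Also, because significant is undefined and no listing is planned, a reader of the study report cannot check which diary entries were carried forward.

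**Working it through.** **1. Is there a planned figure to reproduce?** No. SAP 1.4 states: "No formal power calculations were performed for this study" and "The sample size will consist of up to 50 participants". No document gives an expected rate or number of severe reactions. The rates below are assumptions.

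**2. What severe-only reporting gives if no event occurs.** The exact (Clopper-Pearson) two-sided 95% upper limit for 0 of n is 1 − 0.025^(1/n). At n = 50 this is 1 − 0.025^(0.02) = 7.1%. Since 50 is a maximum, smaller samples give weaker limits: 8.8% at n = 40, 11.6% at n = 30 and 16.8% at n = 20. With 1/50 the interval is 0.1% to 10.6%; with 2/50 it is 0.5% to 13.7%.

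**3. How likely is a count of zero or one?** With true rate p per participant and n = 50, P(0) = (1 − p)^50 and P(0 or 1) = (1 − p)^50 + 50p(1 − p)^49.

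| Assumed p | P(0) | P(0 or 1) |
|---|---|---|
| 1% | 0.605 | 0.911 |
| 2% | 0.364 | 0.736 |
| 5% | 0.077 | 0.279 |
| 10% | 0.005 | 0.034 |

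Setting P(0 or 1) = 0.5 gives p of about 3.3% at n = 50 (4.2% at 40, 5.5% at 30, 8.3% at 20). Zero or one is the more likely outcome only below that rate.

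**4. What the unused data would give.** The counts here are illustrative. A reaction reported by 20 of 50 would be 40% (exact 95% CI 26.4% to 54.8%); by 30 of 50, 60% (45.2% to 73.6%). That is enough to describe a common reaction.

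**5. What the form can support.**
- Apart from erythema and induration, the listed items are yes/no with no grade, so Grades 1 and 2 cannot be read from them.
- Erythema can be placed in the Table 5 diameter bands (2.5–5.0, 5.1–10.0 and over 10.0 cm) after converting from mm.
- Induration cannot be fully graded from the diary: Table 5 note b also requires the functional scale, which the form does not record.
- Protocol 6.9 says the diary collects systemic items that the form does not name, such as headache, muscle weakness and rash (the nearest entry is itching and hives).

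**The case against.** The strongest reply is that this is a deliberate and consistent choice. The protocol itself limits reaction endpoints, events of special interest and the named eCRF content to severe or serious events, and the SAP carries that out. This is a second phase 2 study at the same dose. The protocol reports that the earlier study found the dose well tolerated, and that 372 naive participants were studied at this dose level. The ultimate goal is plasma for BabyBIG. No objective or endpoint uses the word tolerability, and Table 5 note a asks for the diameter to be recorded, not analysed.

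Much of this stands. A reader might infer that the SAP throws away data the protocol meant to analyse. The documents do not support that: the scope is the protocol's, the diary is reviewed at Week 1, and a SAP edit alone would not put the data into the eCRF. A reader might also infer that the trial's safety report will contain severe reactions and nothing else. It will not: SAP 8.1 to 8.4 also cover SAEs of any grade, serious new onset chronic illnesses, abnormal hematology at Week 4, and listings of concomitant medications and vital signs.

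What the reply does not remove is the mismatch between a title and methodology that name tolerability and a plan that leaves the common reactions undescribed. Nothing in the protocol forbids listing the diary, and Protocol 8.2.1 says that data will be listed by participant.

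**Conclusion.** The point holds as a reporting gap that begins in the protocol and is completed by SAP 8.5. Non-serious mild and moderate diary reactions will be neither summarised nor listed, whatever the severe-reaction rate turns out to be. If no severe reaction occurs among 50 participants, the reaction result is 0/50 with an upper limit of 7.1%.

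It is tempting to add that the result will probably rest on zero or one event. The documents do not support that, because they give no rate. Exclusion of people with certain prior severe reactions and the mostly mild or moderate history make a low count plausible, but the statement fails at 5% or more. It must stay conditional on an assumed rate.

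The primary immunogenicity endpoint is unaffected. This is a cheap improvement.

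**What to change.** 1. Replace the last sentence of SAP 8.5 so that all diary data are entered in the eCRF and listed by participant. This also removes the undefined criterion; if a carry-over rule is kept, define it.
2. Tabulate each yes/no item by day, and for any day in Days 1 to 7, as number and percent with an exact 95% CI. Assign no grade that the form does not record.
3. Summarise maximum erythema and induration diameters as continuous values and by Table 5 diameter band. Label the induration band as diameter-only.
4. Keep the severe-reaction endpoint unchanged as the primary safety summary, and present the diary tables as descriptive.
5. Align the eCRF text in the protocol synopsis and the analysis text in Protocol 8.2.5 with this. Reconcile the Appendix C form with the systemic items that Protocol 6.9 says it collects.

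The cost is added eCRF fields, entry of one diary page for each of at most 50 participants, a small set of descriptive displays, and the matching protocol wording.
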